#### **1.4.5 Rationale for use of Immune-related Response Criteria (irRC) to Guide Clinical Care and Assessment of Clinical Activity**

In prior ipilimumab clinical studies, particularly those in metastatic melanoma, clinical efficacy appears to be characterized by objective tumor response (CR and PR), durable stable disease (commonly lasting 6 or more months in subjects receiving 10 mg/kg ipilimumab), and stable disease evolving to objective response after more than a year of follow-up in the absence of alternative anti-cancer therapy. In addition, melanoma subjects receiving ipilimumab who are found to have new lesions at the first follow-up tumor assessment and who are therefore scored as progressors by the mWHO or RECIST criteria have been observed to have stable or decreasing tumor burden in spite of the presence of new lesions. Subjects with such “mixed responses” have been reported to go on to continued reduction in tumor burden in the absence of alternative anti-cancer therapy and objective tumor response by any measure.

The irRC were developed to provide a guide for clinical care of subjects on immunotherapy. Subjects with stable (irSD) or significantly decreasing (irPR) tumor burden despite the presence of new lesions remain on study and continue to receive study drug. Subjects with increasing tumor burden (irPD) are declared progressors and taken off study drug. To account for the various spectra of patterns of new lesions, measurable new lesions are added to the calculation of tumor burden (e.g. added to the SPD of the index lesions). Thus, subjects with many large new lesions will be scored as irPD even if the index lesions are stable or decreasing.

#### **1.4.6 Rationale for use of Blood and Tumor Tissue Biomarkers**

Previous ipilimumab studies explored in their main study design a variety of potential biomarkers in melanoma patients. Results from studies CA184004 and CA184007 suggested the possible biomarkers listed below for further research:

- An increase in peripheral-blood Absolute Lymphocyte Count (ALC) was associated with benefit (Best Overall Response of Complete Response, Partial Response, or prolonged Stable Disease (SD), i.e. SD lasting at least 24 weeks from first dose) and occurred in a dose-dependent fashion favoring 10 mg/kg ipilimumab. In addition to change in ALC over time, ALC value just prior to a third dose of ipilimumab also was associated with benefit.

We will also evaluate FOXP3 and IDO tumor tissue expression at baseline as predictive of clinical benefit, as well as flow cytometry of CD4 and CD8 T cells for Ki67, EOMES and ICOS, predictive markers that have been found to be associated with benefit using ipilimumab. Serum cytokine assays with a multiplex analysis for IL-6, IL-10 and gamma interferon will be conducted, as well as T cell intracellular staining for those cytokines and assessment of allo MLR reactivity as a marker of T cell integrity.

[figure not shown]
A mean increase in the percentage of activated (HLA-DR+), CD4+ and CD8+ T cells and central memory (CD45-RO and CCR9+) T-cells and a mean decrease in percent of naive CD4+ and CD8+ T-cells in Week 4 and Week 12 post-ipilimumab treatment samples has been observed in several studies. Based on these results, a biomarker plan is included in this trial which allows sample collection for biomarker analyses to determine the effects of PANOBINOSTAT on the immune-regulatory effects of ipilimumab treatment. Subjects will

be asked to give blood samples, serum and/or tumor tissue samples for predictive, pharmacodynamic and exploratory biomarker research.

[figure not shown]
## 1.5 Overall Risk/Benefit Assessment

Pan-HDIs have been shown to have antitumor activity both *in vitro* and *in vivo*. In addition to inducing cell cycle arrest and apoptosis of tumor cells, these compounds are also endowed with immunoregulatory properties. For instance, the pan-HDI TSA has been shown to up-regulate MHC and costimulatory molecules on melanoma cells, making them more susceptible to attack by IFN- $\gamma$  secreting T-cells. In addition, Vo et al. have demonstrated that *in vivo* treatment of melanoma bearing mice with the hydroxamic acid analogue pan-HDI LAQ824, significantly augment the anti-melanoma activity of adoptively transferred antigen-specific T-cells. Furthermore, studies in our lab have shown that LAQ824 inhibits the production of IL-10 in APCs rendering these cells more inflammatory and capable of effectively prime naïve antigen-specific CD4+ T-cells and able of restoring the responsiveness of tolerant T-cells (Wang et al. [\*J Immunol.\* 186\(7\): 3986-96, 2011](#)

Panobinostat (LBH589) which is a potent cinnamic hydroxamic acid analog deacetylase inhibitor, induces apoptosis in multiple tumor cell lines *in vitro* at nanomolar concentrations. Panobinostat belongs to the same family of hydroxamic acid derivatives than LAQ824, but has the following advantages: **(i)** It is an oral agent, **(ii)** Clinical studies in humans have shown that panobinostat has a better safety profile than LAQ824 (which was removed from further clinical development due to cardiac toxicity) and, **(iii)** LBH displays more potent HDAC inhibition than LAQ824 both *in vitro* and *in vivo*. Indeed, recent studies in our lab have confirmed that LBH589 is more potent than LAQ824 in inhibiting the proliferation of B16 melanoma cells *in vitro* (**Fig. 1A**). Of note, panobinostat-treated B16 cells are rendered immunogenic due to their enhanced expression of MHC class I and II molecules and the costimulatory molecule CD40 (**Fig. 1B**). In addition to its effect upon melanoma cells, panobinostat also influences the inflammatory status of APCs since treatment of these cells resulted in a dose-dependent inhibition of IL-10 that is accompanied by increased production of the pro-inflammatory cytokine IL-12 (**Fig. 1C**). These inflammatory APCs are in turn, better activators of naïve antigen-specific CD4+ T-cells *in vitro* (**Fig. 1D**).

The results above with LBH589 have been recently extended into human melanoma studies. First, *in vitro* treatment of several human melanoma cells, including BRAF WT (SKMEL21), BRAF mutants (WM983A, WM35 and WM164) or melanoma cells with constitutively activated STAT3 (WM793), with nanomolar doses of LBH589 resulted in a dose dependent inhibition in cell growth (**Fig. 2A**). Cell lines WM983, SKMEL21 and WM793 were the most sensitive to LBH589. Of note, normal melanocytes (HEMn-LP) were not affected by LBH589 at all the doses evaluated. Second, exposure of human melanoma cells to LBH589 resulted in cell cycle arrest in G1 (**Fig. 2B**) and induction of apoptosis (**Fig. 2C**) as demonstrated by increased cleaved PARP in LBH589-treated WM793 and WM983A cells. Third, treatment with LBH589 resulted in increased expression of MHC class I and the costimulatory molecules CD80, CD86 and CD40 in WM983A human melanoma cells (**Fig.2D**).

The immunomodulatory effects of panobinostat upon melanoma cells, APCs and T cells together with the demonstration by others that panobinostat inhibits STAT3, a transcriptional activator of IL-10, and induces changes in CCL22 that allow for Th1 polarization points to this HDI as a novel immune adjuvant with the potential to enhance the therapeutic efficacy of immune stimulating agents like anti-CTLA4 antibodies for the treatment of melanoma. Indeed, we recently treated B16 melanoma bearing mice with anti-CTLA4 antibodies alone, LBH589 alone or a combination thereof. The therapeutic regimen combining panobinostat and CTLA4 blockade significantly delayed melanoma growth *in vivo* as compared to either agent alone shown in **Fig 1E**.

Currently available treatment options for advanced melanoma including Ipilimumab and Vemurafenib, as well as high-dose interleukin-2, produce a spectrum of significant toxicities while providing meaningful clinical benefit. Demonstration of significant clinical responses and prolonged overall survival in subjects with advanced melanoma with the mutant selective inhibitor vemurafenib (PLX4032) has provided clinical validation for mutated B-RAF as a therapeutic target in this tumor type. Duration of response with this agent as monotherapy, however, appears to be limited. Ipilimumab is a potent immunomodulatory agent that has already demonstrated durable clinical benefit and benefit in overall survival in subjects with advanced melanoma. When considered together with the data on observed additive/synergistic anti-tumor activity and promotion of its immune effects in nonclinical studies and their distinct mechanisms of action, administration of panobinostat in combination with ipilimumab can provide a novel treatment regimen that could have the potential to provide significant sustained clinical benefit in this subject population. Potential benefits from this combination, therefore, outweigh the potential risks for toxicity. Assessment of safety and tolerability of panobinostat has been addressed in a monotherapy

study. In this study, panobinostat monotherapy has been administered to over 50 subjects, and continues to exhibit an acceptable tolerability profile that supports its further exploration. There is also preliminary evidence of clinical activity by way of subjects with advanced cancer continuing with panobinostat administration for prolonged periods of time. Principal AEs related to panobinostat administration in the clinic have comprised of constitutional symptoms including fatigue, nausea, diarrhea, vomiting, anorexia, skin rash and decreased appetite. These events are easily monitored by protocol defined clinical assessments (scheduled physical examinations, repeated vital sign measurements, and clinical laboratory assessments) and/or can be managed by supportive measures in conjunction with protocol-specified dose modifications. No eye disorders associated with changes in the retina or the optic nerve have been reported in the clinic to date, as was observed among individual animals at high doses in the nonclinical studies. Given the superficial nature of these lesions, this finding is not considered prohibitive to continued evaluation of panobinostat in the clinic. The most common adverse events with ipilimumab are inflammatory in nature, presumably related to the immune-based mechanism of action, correlated with clinical activity and nearly always reversible with medical management. The most frequently reported drug-related adverse events include diarrhea, colitis, endocrinopathies, hepatitis, and rash. There is potential for overlapping GI toxicity with the combination. Appropriate monitoring plan and guidance on early intervention and management of these events, as well as dose modification guidelines have been included in the protocol. In order to minimize the overall risks to participating subjects, this protocol has inclusion-exclusion criteria appropriate to the population and proposed dosing regimens, exclusionary screening tests, and specific follow-up safety assessments. Based on the potential adverse event profile, appropriate clinical, laboratory, and management algorithms have been incorporated into the protocol. The adverse events (AEs) and serious adverse events (SAEs) will be reviewed on an ongoing basis by the PI and the clinical research team and will be reviewed periodically with an independent DMC to look for trends and any safety issues. Since both PANOBINOSTAT and ipilimumab are experimental agents, it is possible that unforeseen, unknown, or unanticipated reactions can occur during the study.

## **2 ETHICAL CONSIDERATIONS**

### **2.1 Good Clinical Practice**

This study will be conducted in accordance with Good Clinical Practice (GCP), as defined by the International Conference on Harmonisation (ICH) and in accordance with the ethical principles underlying European Union Directive 2001/20/EC and the United States Code of Federal Regulations, Title 21, Part 50 (21CFR50). The study will be conducted in compliance with the protocol. The protocol and any amendments and the subject informed consent will receive Institutional Review Board/Independent Ethics Committee (IRB/IEC) approval/favorable opinion prior to initiation of the study.

Study personnel involved in conducting this study will be qualified by education, training, and experience to perform their respective task(s). This study will not use the services of study personnel where sanctions have been invoked or where there has been scientific misconduct or fraud (eg, loss of medical licensure, debarment).

## **2.2 Institutional Review Board/Independent Ethics Committee**

Before study initiation, written and dated approval from the IRB/IEC will be obtained for the protocol, consent form, subject recruitment materials/process (eg, advertisements), and any other written information to be provided to subjects. The investigator will also provide the IRB/IEC with a copy of the Investigator Brochure or product labeling information and any updates.

The investigator or sponsor will provide the IRB/IEC with reports, updates and other information (eg, expedited safety reports, amendments and administrative letters) according to regulatory requirements or institution procedures.

## **2.3 Informed Consent**

Investigators will ensure that subjects, or, in those situations where consent cannot be given by subjects, their legally acceptable representatives, are clearly and fully informed about the purpose, potential risks, and other critical issues regarding clinical studies in which they volunteer to participate. The informed consent form will adhere to the ethical principles that have their origin in the Declaration of Helsinki.

# **3 INVESTIGATIONAL PLAN**

## **3.1 Study Design and Duration**

This is a Phase 1 open label study of panobinostat administered in combination with ipilimumab. Subjects with unresectable Stage III or Stage IV melanoma who meet the eligibility criteria will undergo screening evaluations within 28 days prior to initiation of study therapy. The study will consist of a dose escalation assessment of the safety and tolerability of oral panobinostat administered concurrently in combination with ipilimumab. Treatment will be divided into induction with ipilimumab and panobinostat and a maintenance phase with panobinostat alone consistent with the general principles of ipilimumab therapy. It is anticipated that this evaluation will enable selection of the RP2D of this combination for further clinical testing. A study schematic is presented below:

Each treatment cycle will be 42 days (6 weeks) during the induction phase, and 84 days (12 weeks) during the maintenance phase. Panobinostat will be administered orally TIW on Days 1-42 of each 42 day treatment cycle. Ipilimumab will be administered intravenously (IV) once every 3 weeks on Days 1 and 22 of each treatment cycle. The induction phase will last for up to 2 treatment cycles. During the maintenance phase, panobinostat will be administered orally TIW on Days 1-84 of each 84 day treatment cycle. Subjects will continue maintenance panobinostat treatment with their designated combination dose regimen until progression of disease, discontinuation due to toxicity, withdrawal of consent or any other reason as specified in Section 3.4.

**Table 3.1 Dose Escalation regimen for Panobinostat and Ipilimumab**

Dose Cohort	Panobinostat Dose	Ipilimumab Dose
1	5 mg po TIW	3 mg/kg
2	10 mg po TIW	3 mg/kg
3	15 mg po TIW	3 mg/kg
4	20 mg po TIW	3 mg/kg
-1	5 mg po TIW	1 mg/kg

**Dose escalation:** Subjects will be enrolled in successive cohorts of 3. An initial cohort of 3 subjects will be enrolled at the given dose level, and additional cohorts of 3 subjects may be added to the same dose level (e.g. increasing the total number of enrolled subjects from 3 to 6, 9 or 12) based on a modified version of a toxicity probability interval (TPI) design introduced by Ji et al. The modified TPI (mTPI) design uses Bayes rule in a decision theoretic framework to determine the MTD based on a target toxicity (eg, dose limiting toxicity; DLT) probability  $P_T$ . A fixed number of subjects, 36, will be used during this dose escalation study. As the dose escalation proceeds under this design, the number of subjects enrolled at a given dose level depends on the number of the toxicities observed at that dose such that multiple cohorts of 3 subjects each may be enrolled to enable a dose escalation decision. The MTD is selected at the end of dose escalation as the dose with an observed toxicity rate closest to the pre-specified target toxicity probability  $P_T$ . In this study, an 18% target toxicity ( $P_T$ ) is used. Background rationale as basis for selection of this target toxicity has been previously outlined in Section 1.4.6. Dose escalation will evaluate panobinostat at doses ranging from 5 to 20 mg TIW administered in combination with ipilimumab at a dose of 3 mg/kg. The first cohort will receive panobinostat orally at a dose of 5 mg PO TIW; ipilimumab will be administered IV at a dose of 3 mg/kg. Enrollment of successive cohorts of subjects will proceed with administration of escalating doses of panobinostat in combination with ipilimumab. Additional dose levels of panobinostat beyond the 20 mg PO TIW dose cohort may be added if appropriate based on the safety and tolerability profile of the combination, and after consultation and agreement between Investigators and Novartis. It is expected that all subsequent dose levels of panobinostat will be no more than 33% higher than the preceding dose. If the first dose cohort is demonstrated to have unacceptable toxicity, dose level -1 will be instituted with 5 mg PO TIW of panobinostat and ipilimumab at 1 mg/kg.

**There will be no intra-subject dose escalation.** Decisions regarding dose escalation between cohorts will be guided by the incidence of drug-related dose limiting toxicities (DLTs) occurring within 84 days (12 weeks; through Day 42 of induction cycle 2) of initiation of study therapy. If three patients complete their 84 day period of treatment without DLT, then at least three additional patients must exceed 9 weeks without MTD being reached to be able to dose escalate. This DLT observation interval is based upon inclusion of the known median times to onset of common immune-related adverse events attributed to ipilimumab (see Section 4.3.5.1) and allows for a substantial amount of time for unexpected toxicities with the combined administration of panobinostat and ipilimumab to emerge. Subjects who do not complete the DLT observation period for reasons other than drug-related toxicity will be replaced. One of the following five decisions will be made at the end of the DLT period for each cohort of 3 subjects based on the number of DLT's observed:

- S: stay at the same dose and enroll a cohort of 3 more subjects at that dose
- E: escalate to the next higher dose by enrolling 3 more subjects
- D: de-escalate to the lower dose, and enroll 3 more subjects at the lower dose, or
- DU: declare the current dose as unacceptable and unsafe, de-escalate to the lower dose, and enroll 3 more subjects at the lower dose
- C: Study completed and dose is declared to be the MTD

Decisions S or E are allowed by the design if determined that the corresponding doses are safe based on the target toxicity. Decisions D or U are based on evidence of exceeding predetermined toxicity. With a target toxicity rate of 18%, allowing any dose with estimated  $P_T$  in the (17%, 19%) interval to be selected as the MTD in this study, and with a maximum fixed total of 36 subjects at the dose escalation phase in each arm, the algorithm for dose escalation decisions based on possible total number of subjects at each dose cohort is described in Table 3.2 below.

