target toxicity (eg, dose limiting toxicity; DLT) probability  $P_T$ . A fixed total number of subjects will be used during the dose escalation portion for each arm. As the dose escalation proceeds under this design, the number of subjects enrolled at a given dose level depends on the number of the toxicities observed at that dose such that multiples of 3 subjects each may be enrolled to enable a dose escalation decision. The MTD is selected as the dose with an observed toxicity rate closest to the pre-specified target toxicity probability  $P_T$ . In this study, a tight 18% target toxicity ( $P_T$ ) is used.

Dose escalation will evaluate panobinostat at doses ranging from 5 to 20 mg thrice weekly administered in combination with ipilimumab at doses of 3 mg/kg. The first cohort will receive panobinostat orally at a dose of 5 mg thrice weekly; ipilimumab will be administered IV at a dose of 3 mg/kg. Enrollment will proceed with administration of escalating doses of panobinostat in combination with ipilimumab as described in Table 1 below:

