Note that decisions S or E are allowed by the design when determined that the corresponding doses are safe based on the target toxicity. Decisions D or DU are based on evidence of exceeding predetermined toxicity. With a target toxicity rate of 18%, allowing any dose with estimated  $P_T$  in the (17%, 19%) interval to be selected as the MTD in this study, and with a maximum fixed total of 12 subjects at the dose escalation phase in each arm, the algorithm for dose escalation decisions based on possible total number of subjects at each dose cohort is described in Table 3.2.

Based on the above design, escalation to the next higher dose level can occur if DLTs are observed in 0 of 3 or 1 of 6 subjects, in up to 2 of 12 subjects, and so on. If DLTs are observed in a greater number of subjects and escalation is not yet permitted, additional subjects in cohorts of 3 will be enrolled at the same dose in order to better estimate the true DLT rate at that dose until either the dose is deemed safe and an escalation is allowed, the dose is deemed unacceptable and should not be used, or de-escalation is recommended, based on decision rules outlined in Table 3.2. At the end of the dose escalation phase, the MTD will be estimated by isotonic regression or another Bayesian model-based approach (eg logistic regression) using observed toxicities at all studied doses.

The combination dose with posterior probability of toxicity closest to the target toxicity,  $P_T$ , will be declared as the MTD.

The dose escalation plan (see table above) uses a modified  $J_i$  design, with dose escalation decisions made every three patients. The trial will enroll 36 patients for determination of the MTD, but will be successfully concluded earlier if 12 patients are accrued at the dose determined to be the MTD, with at most 3 toxicities.

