**Table 3.2 Dose Escalation Algorithm for each arm: modified TPI design**

Dose Escalation: This is a Phase I dose escalation trial and the sample size at each dose depends on the observed toxicity, and a total of 36 subjects at the dose-escalation phase allows sufficient number of subjects if needed, e.g. more than 6 subjects if dose-limiting toxicities are observed among 2 of 6 subjects, to better estimate the toxicity rates per dose, and more accurately determine the MTD. Cohorts of 3 subjects with possible expansions to 6, 9, or 12 subjects will be treated at each suggested dose level until MTD is defined.

In this protocol, we will be using a new phase I trial approach (Table 3.2), modified from a design from Ji et al. This approach provides a broader phase I experience than the traditional 3+3 design, thus allowing for a more robust choice of an MTD. While setting the target toxicity rate at 18%, this design allows further examination of a dose when 2 DLTs occur among 6 patients, while still keeping the observed toxicity at the MTD well managed (it is below 26% for sample sizes  $\geq 9$ ). Moreover the MTD will exploit the isotonic nature of dose escalation in determination of the MTD.

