## 8 STATISTICAL CONSIDERATIONS

### 8.1 Sample Size Determination

Dose Escalation: This is a Phase I dose escalation trial and the sample size at each dose depends on the observed toxicity; however a total of 36 subjects for the dose-escalation study allows sufficient number of subjects if needed, e.g. more than 6 subjects if dose-limiting toxicities are observed among 2 of 6 subjects, to better estimate the toxicity rates per dose, and more accurately determine the MTD. Cohorts of 3 subjects with expansions to 6, or possibly even 9 or 12 subjects will be treated at each suggested dose level until MTD is determined.

In this protocol, we will be using a new phase I trial approach (Table 8.1), modified from a design from Ji et al. This approach provides a broader phase I experience than the traditional 3+3 design, thus allowing for a more robust choice of an MTD. While setting the target toxicity rate at 18%, this design allows further examination of a dose when 2 DLTs occur among 6 patients, while still keeping the observed toxicity at the MTD well managed (it is below 26% for sample sizes  $\geq 9$ ). The trials will enroll up to 36 patients for determination of the MTD, but will be successfully concluded earlier if 12 patients are accrued at the dose determined to be the MTD, with 3 DLTs. If, at any time, one de-escalates to a dose which has already accrued 12 patients, the study will be terminated and that dose declared to be the MTD. The MTD is obtained at 33 patients if 9 or 12 patients have been accrued at the current dose and the dose is acceptable (E, S or C). Otherwise, if the current dose has  $\leq 1$  of 3, or  $\leq 2$  of 6 DLTs, then three more patients will be accrued at that dose – if at most 1 of 6, or 2 of 9 have DLTs, that dose is the MTD.

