**Table 8.1 Decision Rules on dose escalation based on number of DLTs\*\***

N*	Observed DLTs per cohort and treatment decisions									
	0	1	2	3	4	5	6			
3	E	S	DU	DU	-	-	-	-	-	-
6	E	E	S	DU	DU	DU	DU			
9	E	E	S	D	DU	DU	DU			
12	E	E	E	C	DU	DU	DU			

N\* =number of subjects treated at a given dose level

S: stay at the same dose and enroll a cohort of 3 more subjects at that dose

E: escalate to the next higher dose by enrolling 3 more subjects

D: de-escalate to the lower dose, and enroll 3 more subjects at the lower dose, or  
DU: declare the current dose as unacceptable and unsafe, de-escalate to the lower dose, and enroll 3 more subjects at the lower dose

C: Study completed and dose is declared to be the MTD

\*\*for MTD target toxicity pT=18%, and allowing any dose with pT in (17%, 19%) to be selected

The modifications involve escalating the dose whenever the observed toxicity rate is below 17% and using the N-1st patient to define the change when the toxicity rate exceeds 19% and  $N \geq 9$  to account for the fact that the design is being used in cohorts of 3 rather than continuously as designed by Ji et al.

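### The MTD rule that takes the raw DLT rate closest to 18% conflicts with the plan's other MTD rules; where it decides, it can name a low dose beneath cleared higher doses or, more rarely, a DU-coded dose

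*Combined protocol and SAP*

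**What the plan says.** The plan gives at least three ways to arrive at the MTD.

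- **Raw rate.** Section 3.1 (Dose escalation): "The MTD is selected at the end of dose escalation as the dose with an observed toxicity rate closest to the pre-specified target" probability, with "In this study, an 18% target toxicity". The Synopsis has the same rule: "The MTD is selected as the dose with an observed toxicity rate closest to the pre-specified target toxicity probability". Neither sentence uses dose order or the decision codes.
- **Isotonic or model-based estimate.** The Synopsis, after Table 1, says "the MTD will be estimated by isotonic regression or another Bayesian model-based approach (eg logistic regression) using observed toxicities at all studied doses", and makes the MTD "The combination dose with posterior probability of toxicity closest to the target toxicity". Section 3.1, in the text headed Table 3.2, adds: "Moreover the MTD will exploit the isotonic nature of dose escalation in determination of the MTD". No tie rule is given, and no dose is excluded from the selection.
- **Accrual and codes.** Under Table 8.1, 3 DLTs in 12 is code C and makes that dose the MTD. Section 8.1 also declares the MTD when the trial de-escalates to a dose that already has 12 patients, and when 33 patients have been treated and the current dose has 9 or 12 patients and code E, S or C. A further rule covers one last cohort of three.

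Table 8.1 defines "DU: declare the current dose as unacceptable and unsafe, de-escalate to the lower dose". Section 8.1 says of the design: "while still keeping the observed toxicity at the MTD well managed (it is below 26% for sample sizes" of at least 9). The Synopsis makes a unique MTD the recommended Phase 2 dose.

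**The concern.** The MTD is the primary result, and these rules can name different doses from the same data. The raw rule is the weakest of them. Distance from 18% on unsmoothed rates in 3 to 12 patients lets one chance DLT at a low dose outweigh cleaner results at higher doses. It also penalises 0% more than 33.3%, so a dose that the table has just rejected can win. Without a stated order of precedence, the choice of rule would be made after the DLT counts are known.

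**Working it through.** **Inputs.** Target 18% (Section 3.1). Codes from Table 8.1: N=3: 0 E, 1 S, 2–3 DU; N=6: 0–1 E, 2 S, 3 or more DU; N=9: 0–1 E, 2 S, 3 D, 4 or more DU; N=12: 0–2 E, 3 C, 4 or more DU. Maximum 36 patients (Section 8.1). Distance = |x/N − 0.18|.

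**1. The plan's own figure.** The highest rates among acceptable cells (E, S, C) are 2/9 = 22.2% and 3/12 = 25.0%. The statement that the rate at the MTD stays below 26% for N of at least 9 therefore reproduces for acceptable cells. It does not hold under the raw rule, which can name 4/12 = 33.3%.

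**2. A low dose beneath cleared doses.** Take cohorts 1–4 at 1/6, 0/6, 0/6, 1/12, all coded E.
- Distances: |0.167 − 0.18| = 1.3 points, 18.0, 18.0, and |0.083 − 0.18| = 9.7. The raw rule names cohort 1.
- Isotonic fit: cohorts 1–3 pool to 1/18 = 5.6% and cohort 4 stays at 8.3%, so cohort 4 is closest.
- With 0/3 in place of 0/6 at cohorts 2 and 3, the isotonic fit is 1/12 = 8.3% at all four doses: a tie with no rule to break it.

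**3. A DU-coded dose.** Cohort 1 is 0/3 (E). Cohort 2 runs 1/3 (S), 2/6 (S), 2/9 (S), 4/12 (DU). Cohort 1 is then filled to 0/12.
- Distances: |0 − 0.18| = 18.0 and |0.333 − 0.18| = 15.3. The raw rule names cohort 2.
- The isotonic estimates are 0% and 33.3%, so isotonic estimation alone names the same dose.
- Other DU cells lie further from target than a 0% dose: 2/3 48.7, 3/6 32.0, 4/9 26.4, 5/12 23.7 points. While another tried dose is not DU, the failure is essentially 4/12 with no DLTs at every other tried dose.

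**4. Does Section 8.1 step in?** Example 2 ends at 6+6+6+12 = 30 patients with code E at the top dose. Example 3 ends at 12+12 = 24 with code E beneath a DU dose; cohort 1 had only 3 patients when the trial de-escalated to it. There is no 3/12, no de-escalation to a dose with 12 patients, and no 33-patient point, so the end-of-escalation rule decides. In simulation this is so in roughly 60–78% of trials.

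**5. Simulation of Table 8.1, Section 8.1 declarations applied first** (20,000 trials per scenario). Assumptions where the plan is silent: true rates as shown; code E at the top dose or below a DU dose means enrolling to 12; a DU dose bars higher doses; cohort −1 is not modelled; raw-rule ties go to the lowest tied dose. The fix sends ties to the highest dose if the tied estimate is at or below 18%, otherwise to the lowest.

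| True rates, cohorts 1–4 | True 18% dose named: raw rule | With fix |
|---|---|---|
| 2/5/10/18% | about 48% | about 73% |
| 5/10/18/30% | about 38% | about 43% |
| 10/18/30/40% | about 38% | about 43% |

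Across these scenarios the raw rule named a dose below a cleared dose (n of at least 6, equal or lower rate) in about 15–34% of trials. It named a DU dose in about 1.5–5%, and in about 7% at 5/30/45/60%. Part of the DU figure is trials in which every tried dose is DU; the 4/12 pattern itself accounts for about 2% in each of the three scenarios.

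**6. Sensitivity to raw-rule ties.** Several doses at 0% tie under the raw rule. A rerun with ties going to the highest dose gives about 63/42/41% correct and about 5–13% for the low-dose failure. If Section 3.1 is read as requiring six patients before escalation, the low-dose failure is about 21–43% with ties low and 9–21% with ties high.

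**The case against.** The strongest reply is that no one would apply the raw sentence alone. The Synopsis and Section 3.1 already call for dose order. The text around Table 3.2 says that an unacceptable dose should not be used. Section 8.1 ties several declarations to acceptable codes, and its 26% figure shows that the authors had acceptable cells in mind. All of this is correct, and it rules out the stronger reading that a reader might infer: that the raw rate is the plan's only MTD rule and that the plan therefore sets out to recommend unsafe doses. What remains is that the isotonic rule still selects the 4/12 dose and has no tie rule, that the statement about unacceptable doses sits in the enrolment rules and not in MTD selection, and that Section 8.1 is silent in many trials.

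A second reply uses the Synopsis sentence on early conclusion with 12 patients at the MTD and at most 3 toxicities. If that means that the current dose with 12 patients and 3 or fewer DLTs is the MTD, both examples resolve. A simulation on that reading gave 73/43/41% correct and neither failure. But the sentence presupposes that the MTD is already determined, Section 8.1 states the same condition with exactly 3 DLTs, and Table 8.1 codes 0–2 of 12 as E. The reading is possible but not written as a rule.

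Third, the direction of the tie rule is partly a risk preference. This stands: much of the simulated gain depends on how ties are handled.

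**Conclusion.** The concern holds as a conflict between rules with real consequences where the raw rule decides. Naming a low dose beneath cleared ones is the common failure (about 15–34%, or about 5–13% if raw ties go up). Naming a DU dose is narrow (about 1.5–5%, about 7% on a steep curve), and isotonic estimation alone does not prevent it. These sizes rest on assumed true rates and on the conventions listed above; the arithmetic of the two examples does not.

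Two further inferences are not supported. A reader might add 3/9, coded D, as another rejected dose that the raw rule would name; with no DLTs at the lower doses, the trial would normally re-escalate or meet a Section 8.1 stop, so 3/9 would seldom be final. A reader might also call the 26% statement wrong; it is right for acceptable cells and fails only if the raw rule is allowed to override the codes. The point deserves correction before data accrue, but its weight should not be argued as if the raw rule acted alone.

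**What to change.** In the Synopsis (Dose escalation, before and after Table 1), Section 3.1 and Section 8.1, reconcile the rules and state one governing order:

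1. The Section 8.1 and Table 8.1 declarations apply first.
2. Otherwise, use the isotonic estimate already named in the Synopsis in place of the raw rate. Limit candidates to doses not coded D or DU at the end and lying below any DU dose, and prespecify a tie rule.
3. State the outcome if no dose qualifies, including how cohort −1 enters.

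The Synopsis sentence on 12 patients with at most 3 toxicities should be aligned with Section 8.1 at the same time.

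The cost is a few sentences and two statistical trade-offs. A dose above the target is named somewhat more often: at 5/10/18/30%, comparing the selection rules without the Section 8.1 declarations, a true-30% dose was named in 25% of trials against 15%. Where cohort 1 is itself the 18% dose, it is selected less often (about 42–47% against 67–75%), partly because the raw rule names a cohort 1 already coded D or DU. The team should rerun the operating characteristics under its chosen tie rule, with cohort −1 included.
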